### 14.6.2 Analysis of Secondary Efficacy Endpoints

For all secondary endpoints, no official statistical hypothesis will be tested, and statistical comparisons may be conducted for exploratory purposes only.

- For the total number of bowel movements per week at week 1 and for the whole week 2 period, similar methods to those described for the primary endpoint will be used.
- The mean daily stool form score according to BSFS will be summarized over time by treatment dose using descriptive statistics. The mean daily score during the first week, second week and during the whole 2-week period of treatment will be compared to the baseline score using the paired Student's t-test or the Wilcoxon signed rank test, as appropriate based on the data distribution.
- For the total number of bowel movements with a BSFS  $\geq 6$  after 1 and 2 weeks of treatment and for the Mean Diarrhea Composite Index, descriptive statistics will be used by treatment dose. Within-group comparisons with the baseline values and between-group comparisons will be conducted as described in the primary endpoint.
- The proportion of patients treated with loperamide will be described by treatment dose and among treated patients the mean daily dose of loperamide in mg will be summarized.
- Overall evaluation of diarrhea, abdominal pain, urgency and bloating will be summarized over time by treatment dose using descriptive statistics. Within-group comparisons with the baseline score will be conducted using the paired Student's t-test or the Wilcoxon signed rank test, as appropriate.

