## **6. STUDY OBJECTIVES**

### **6.1 Primary Objective**

The primary objective of this study is to investigate the clinical efficacy of new ECC capsules and select the most effective dose in adult patients with SBS.

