#### **7.1.2 Justification for the Primary Endpoint**

Several efficacy endpoints have been used in the study of the use of cholestyramine or other bile acids sequestrants in the management of bile acid diarrhea (BAD). These included fecal weight, fecal volume, weekly frequency of bowel movement (typically called 'number of stools' in the literature), mean stool type according to the Bristol Stool Form Scale (BSFS), loperamide use, etc. In a clinical trial in primary and secondary BAD, Walters *et al.* used an innovative

index taking into consideration the weekly stool frequency, the mean BSFS, as well as loperamide use (29). This index was: (weekly stool frequency X mean BSFS) + loperamide use. This index, while non-validated *per se*, was justified by the variable nature of BAD symptoms. All components of this index were influenced by the study treatment, obeticholic acid, in BAD patients.

Weekly stools (bowel movement [BM] frequency) is an objective endpoint that can be easily measured by patients, using a diary. BSFS can be more difficult to assess by study subjects, since it implies a visual evaluation of the stools and is consequently more subjective. Fecal weight and volume require regular stool collection, which is cumbersome.

In light of these considerations, the weekly number of bowel movements is proposed as the study primary efficacy endpoint. This endpoint is clinically relevant to the symptom of diarrhea, and an increased frequency translates to a decreased water reabsorption as well as an accelerated GI transit, both important pathogenic components of SBS. The data obtained from Walters and other authors show that bowel movement frequency (stool frequency) is a sensitive index for pharmacological intervention in SBS. While significant variability can be observed with this parameter, weekly bowel movement frequency can be greatly reduced by antidiarrheal drugs and bile acids modulating agents (e.g. obeticholic acid). Moreover, the second week of treatment with ECC will be used for this purpose, in order to reach an expected maximum and stable effect at each dose of the drug studied.

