### 7.1.3 Secondary Endpoints

- Total number of bowel movements per week, after the first week of treatment (i.e. Days 1 to 7, and Days 29 to 35)
- Total number of bowel movements for the whole 2-week treatment period (i.e. Days 1 to 14 and Days 29 to 42)
- Mean daily stool form score according to the BSFS, measured during the first week of treatment (i.e. Days 1 to 7, and Days 29 to 35)
- Mean daily stool form score according to the Bristol Stool Form Scale (BSFS), measured during the second week of treatment (i.e. Days 8-14, and Days 36-42)
- Mean daily stool form score according to the BSFS, measured during the whole 2-week treatment period (i.e. i.e. Days 1 to 14 and Days 29 to 42)
- Total number of bowel movements with a BSFS score  $\geq 6$  during the first week of treatment (i.e. Days 1 to 7, and Days 29 to 35)
- Total number of bowel movements with a BSFS score  $\geq 6$  during the whole 2-week treatment period (i.e. Days 1 to 14 and Days 29 to 42)
- Mean daily dose of loperamide in mg, if used, during the second week of treatment (i.e. Days 8-14, and Days 36-42)
- Mean Diarrhea Composite Index ([weekly BM frequency X mean daily BSFS score] + loperamide use [weekly mg X 3]) during the second week of treatment (i.e. Days 8-14, and Days 36-42)
- Safety (to be evaluated through the assessment of AE, laboratory tests, vital signs, ECG and physical examination)
- Tolerability (to be evaluated through assessment of TEAEs and TESAEs)

[figure not shown]
Overall evaluation of diarrhea, abdominal pain, urgency and bloating using an 11-point Visual Analog Scale (VAS) made on Days 0 (baseline), 15, 28 and 43

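### Section 14.6.2 tests the mean daily BSFS score and the four VAS symptoms only against baseline and specifies no comparison of the two doses for these seven measures

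*Combined protocol and SAP*

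**What the plan says.** Section 14.6.2 handles the secondary endpoints in separate bullets, and the contrasts differ between them.

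- **Bowel-movement counts** follow the primary methods. Those include the paired High-versus-Low test in step c of Section 14.6.1.
- **Mean daily BSFS score** for week 1, week 2 and both weeks is summarised by dose and "will be compared to the baseline score using the paired Student's t-test or the Wilcoxon signed rank test, as appropriate based on the data distribution".
- **Counts of stools with BSFS of 6 or more, and the Diarrhea Composite Index**: "Within-group comparisons with the baseline values and between-group comparisons will be conducted as described in the primary endpoint".
- **The four VAS symptoms**: "Overall evaluation of diarrhea, abdominal pain, urgency and bloating will be summarized over time by treatment dose using descriptive statistics". The only test is then: "Within-group comparisons with the baseline score will be conducted using the paired Student's t-test or the Wilcoxon signed rank test, as appropriate".

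The section opens with a general qualifier: "For all secondary endpoints, no official statistical hypothesis will be tested, and statistical comparisons may be conducted for exploratory purposes only". The primary objective in Section 6.1 includes the aim to "select the most effective dose in adult patients with SBS". Section 6.2 makes symptom experience on the VAS a secondary objective. Section 7.1.2 says of BSFS, in contrast to stool frequency, that "it implies a visual evaluation of the stools and is consequently more subjective".

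**The concern.** Section 7.2.1 gives every patient active drug in both periods, so there is no placebo period against which to read a change from baseline. For a self-rated score that change combines drug effect with expectation and the passage of time. For BSFS it also includes regression to the mean: inclusion criterion 10 selects patients on loose stools in the screening diary, and Section 9.2.1 uses the same diary to establish the baseline.

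The comparison of the two doses is randomised, blinded and within-patient. Selection at screening precedes randomisation and so favours neither dose. Yet for mean daily BSFS and the four VAS symptoms the plan specifies the uncontrolled contrast and omits the controlled one.

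As written, the report could show stool form, urgency, pain and bloating each improved on both doses, with no interval for the difference between doses. Anyone using those results to help choose a dose would lack the figure they need.

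**Working it through.** **1. Which contrasts are specified**

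| Secondary measure | Test against baseline | High versus Low |
|---|---|---|
| Bowel movements, week 1 and the longer period | yes | yes, through the primary methods |
| Stools with BSFS of 6 or more | yes | yes |
| Diarrhea Composite Index | yes | yes |
| Mean daily BSFS: week 1, week 2, both weeks (3 measures) | yes | not specified |
| VAS: diarrhea, pain, bloating, urgency (4 measures) | yes | not specified |

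That leaves 3 + 4 = 7 measures without a dose comparison. If each is tested once per dose, as the by-dose summaries imply, there are 7 × 2 = 14 before-after tests and no specified dose contrast.

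**2. What the by-dose summaries give and omit**

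Let H and L be a patient's scores on the High and Low dose, with standard deviations s_H and s_L and within-patient correlation r.

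- Among patients with both periods, mean(H − L) = mean(H) − mean(L). The point estimate can be read from the two columns.
- Var(H − L) = s_H² + s_L² − 2·r·s_H·s_L. The columns give s_H and s_L but not r, so the paired standard error and interval cannot be recovered.

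**3. No new baseline decision is needed**

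Section 14 defines baseline as the last value before the first dose of study drug. With that common baseline B, (H − B) − (L − B) = H − L. The end-of-period scores suffice.

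**4. The plan's own paired method, reproduced**

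Inputs from Section 14.1: SD 2.0 per treatment, correlation 0.80, significance level 0.05, power 80%.

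- SD of the difference = √(2 × 2.0² × (1 − 0.80)) = √1.6 = 1.265, as stated.
- A two-sided paired t-test reproduces all 16 rows of Table 3, from 81 patients at a difference of 0.40 to 15 at 1.00. Then 15 × 1.2 = 18, the stated total.

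The paired method is therefore already in the protocol and reproduces its sample size.

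**5. What the added comparison could show**

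The documents give no SD for BSFS or VAS, so results are in units of the SD of the within-patient difference. The half-width of the 95% interval is t(0.975, n − 1)/√n. Attrition of 20% leaves 18 × 0.8 = 14.4, or 14 pairs.

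| Complete pairs | Half-width of 95% CI (SD units) | Difference detectable with 80% power (SD units) |
|---|---|---|
| 18 | 2.110/√18 = 0.50 | 0.70 |
| 15 | 2.145/√15 = 0.55 | 0.78 |
| 14 | 2.160/√14 = 0.58 | 0.81 |

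These intervals are wide, but each is an estimate of the dose difference with its uncertainty, which the present plan does not supply.

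**The case against.** The strongest reply is that little depends on these measures. Every secondary comparison is exploratory, and the opening sentence of Section 14.6.2 would allow a High-versus-Low analysis. Dose selection rests mainly on step c for stool frequency, and the VAS belongs to a secondary objective. This stands as a limit on the consequence. It does not justify the choice of contrast: the baseline tests are equally exploratory, and permission to compare the doses is not a specification. Step c covers frequency only and is reached only if steps a and b both succeed.

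A reader might infer that stool form is never compared between doses. The section does not support that. The counts of stools with BSFS of 6 or more have a between-dose comparison, and so does the composite index, which contains mean daily BSFS as a factor. The gap concerns the mean daily score itself and the VAS. The composite mixes form with frequency and loperamide, and no other planned comparison covers pain, urgency or bloating.

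A reader might also infer that the plan misstates the precision of the dose difference by a factor that follows from the correlation of 0.80. That does not hold either. The plan never proposes to treat the two columns as independent, and Section 14.1 assumes that correlation only for changes in bowel movements.

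Two further points stand. Section 14 defers detail to a statistical analysis plan, and the document contains no separate plan text, so the omission is shown for Section 14 alone. The VAS contrast may also be weakly informative: each score is a single 24-hour recall on Day 15 or 43, the day after the last dosing day, with a visit window of one day either way.

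**Conclusion.** The point holds for seven measures: mean daily BSFS in three time windows and the four VAS symptoms. For these, Section 14.6.2 specifies an uncontrolled before-after test and no between-dose comparison, while related endpoints in the same section have one, and no reason is given for the difference.

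The consequence is moderate. No confirmatory claim, error rate or sample size is affected, and the primary endpoint has its dose comparison. What is lost is the interval for the dose difference on symptoms and mean stool form, in a trial whose primary objective includes choosing a dose.

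The conclusion rests on Section 14.6.2 as written and on the absence of a placebo period. It needs no assumption about the correlation or variability of BSFS or VAS scores. The precision figures assume 14 to 18 complete pairs and approximately normal differences.

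**What to change.** In Section 14.6.2, for mean daily BSFS (week 1, week 2, both weeks) and each of the four VAS symptoms, add the within-patient High-minus-Low difference with a 95% confidence interval.

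- Use the matching diary weeks of each period for BSFS, and the Day 15 and Day 43 scores for the VAS.
- Use the paired method of step c in Section 14.6.1, and report the number of patients with both periods.
- State that these estimates are produced whatever the outcome of steps a and b, so that the primary testing sequence does not suppress them.
- Label them exploratory, and describe the change-from-baseline tests on these measures as supportive description.

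The cost is seven more exploratory rows in planned tables, with wide intervals at 18 patients or fewer. No extra patients, visits or data are needed, and no error-rate claim changes.

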## 14.7 Safety Analyses

All safety data will be included in subject data listings. Summary tables will be based on the safety population. No statistical comparisons will be conducted.

### 14.7.1 Adverse Events

AEs will be coded using the Medical Dictionary for Regulatory Activities (MedDRA, version 21.1 or later).

For the purpose of analyses and tabulations, AEs will be classified as pretreatment AEs, TEAEs, or post-treatment AEs. More specifically: Pretreatment AE are those that started before the first dose of study drug. TEAE are those that increased in severity (compared to pre-treatment) or that appeared at or after the first dose of study drug but before the last follow-up of each period. Post-treatment AEs are those that increased in severity or that appeared after the last follow-up, planned for 4 weeks after the last dose of study drug. For AEs with missing or incomplete start dates, if there is no clear evidence that the AEs started before or after the first dose of study drug, then the AEs will be classified as TEAEs.

AE summary tables, including the number and percentage of patients with at least one AE overall and by MedDRA system organ class (SOC) and preferred term (PT), will be presented by treatment group for TEAE only and will include the following: All TEAEs, TEAEs by relationship, TEAEs by maximal severity, TEAEs leading to treatment discontinuation, serious TEAEs and fatal TEAEs. All AEs, including pre- and post-treatment AEs, will be presented in individual patient data listings. For these summaries, patients with multiple events will be counted only once per PT. For the TEAEs by relationship and TEAEs by maximal severity, at each level of summarization, the event with the strongest drug relationship and highest level of severity, respectively, will be presented.

All AEs must be listed. In addition, separate listings will be provided for patients who die, experience a SAE, or discontinue the study because of an AE. These listings will include treatment, patient's age and gender, duration of follow-up, amount of ECC received, and time since last intake.

### 14.7.2 Clinical Laboratory Assessments

Safety laboratory variables (e.g., hematology, biochemistry, and urinalysis results) will be presented in the International System of units at each time point using descriptive statistics (mean, standard deviation, median, minimum, and maximum). Change from baseline values for each variable will also be presented by treatment group. The number and percentage of patients with shift changes from baseline (normal, high, and low according to the reference range as provided by the laboratories) to post-baseline will be tabulated by treatment group.

### 14.7.3 Vital Signs

Vital signs (blood pressure, temperature and heart rate) will be presented at each time point using descriptive statistics (mean, standard deviation, median, minimum, and maximum). Change from baseline values for each variable will also be presented by treatment group.

The number and percentage of patients with shift changes from baseline to post-baseline based on abnormal criteria will be presented by treatment group.

#### **14.7.4 ECG**

For ECG measurements, a summary of raw values at baseline and end of study and change from baseline values will be provided for the following standard digital ECG measurements: PR, QT, and QT corrected for heart rate (QTc) intervals, QRS duration, and HR. The number and percentage of patients with shift changes from baseline (normal, not clinically significant, and potentially clinically significant according to overall ECG evaluation as provided by the laboratories) to end of study will be tabulated.

In addition, the number and percentage of patients with QT/QTc intervals values of  $\leq 500$  msec and  $> 500$  msec, as well with changes from baseline in the value of QT/QTc intervals by  $> 30$  msec will also be tabulated.

### **15. DATA HANDLING AND RECORD KEEPING**

#### **15.1 Case Report Forms**

All patient data generated by the study will be recorded in each patient's e-CRFs. Data reported on the e-CRFs that are derived from source documents should be consistent with the source documents or the discrepancies should be explained. e-CRFs will be considered complete when all missing and/or incorrect data have been resolved and all safety data have been recorded.

The Investigator, or designated representative, should complete the e-CRF as soon as possible after information is collected. e-CRFs must be completed only by persons designated by the Investigator. The e-CRF system should enable an audit trail that will provide the user's identification information and the date and time of any entry/correction. The completed e-CRF will be reviewed by the Sponsor, study monitor or Sponsor's designees on a routine basis.

The Investigator must approve formally (via signature) all the information in the e-CRFs for the patients for whom he/she is responsible.

A copy of the e-CRFs will be provided to the Sponsor with the final report.

Subjects who do not meet protocol criteria will be entered on a screening/enrolment log and no e-CRF will be completed.

#### **15.2 Source Documentation**

Source documents are considered to be all information in original records and certified copies of original records of clinical findings, observations, data, or other activities in a clinical study necessary for the reconstruction and evaluation of the study. The Investigator and designees agree to maintain accurate e-CRFs and source documentation as part of the case histories. Source documents are the originals of any documents used by the Investigator, sub-Investigator, or hospital/institution that will allow verification of the existence of the patient and substantiate the integrity of the data collected during the trial. All data entered into the e-CRF also must be available in the source documents. The Investigator will allow designated representatives of the Sponsor and regulatory bodies to have direct access to the source documents to verify the data reported in the e-CRFs in the course of trial-related monitoring, audits, IRB/IEC review and regulatory inspections.

### 15.3 Record Retention

Study records and source documents must be retained for at least 25 years after the completion or discontinuation of/withdrawal from the study, or 2 years after the last approval of a marketing application in an International Conference on Harmonization (ICH) region, whichever is the longest time period. If it becomes necessary for the Sponsor to review any documentation relating to the study, the Investigator must permit access to such records.

The Investigator should contact the Sponsor before destroying any records pertaining to the study to ensure they no longer need to be kept.

### 15.4 Data Management and Processing

Data management activities will be performed using the Omnicomm Trial Master electronic data capture (EDC) software in accordance with the data management facility's SOPs.

Data entered will be checked for accuracy through QC checks. When the database is declared to be complete and accurate, it will be locked.

## 16. MONITORING

In accordance with current applicable regulations, Good Clinical Practice (GCP), and the Sponsor's Standard Operational Procedures, monitors from the CRO will contact the site before the start of the study to review with the site staff the protocol, study requirements, and their responsibilities to satisfy regulatory, ethical, and Sponsor requirements. When reviewing procedures for data collection, the discussion will include identification, agreement, and documentation of data items which will be recorded in each patient's e-CRF.

The study will be monitored to ensure the following:

- Data are authentic, accurate, and complete;
- The safety and rights of patients are being protected;
- The study is being conducted in accordance with the currently approved protocol, any other study agreements, GCP, and all applicable regulatory requirements.

The Investigator and the head of the medical institution (where applicable) agree to allow the monitor direct access to all relevant documents.

## 17. QUALITY CONTROL AND QUALITY ASSURANCE

The Sponsor's designee will perform the quality assurance and quality control activities of this study. Designated personnel from the quality assurance unit(s) of the clinical facility will be responsible for maintaining QA systems to ensure that the trial is conducted and that clinical data is generated, documented and reported in compliance with the protocol and ICH Guideline E6 for GCP.

Designated personnel from the corresponding operation unit (usually of the clinical and statistical facilities) will be responsible to maintain and assure the quality control (QC) of all data generated and documented in compliance with the protocol. However, responsibility for the accuracy, completeness, and reliability of the study data presented to the Sponsor lies with the principal or qualified Investigator generating the data.

The Sponsor or its designated representative will conduct a study site visit to verify the qualifications of the principal Investigator and sub-Investigators, inspect clinical site facilities as needed, and inform the Investigator of responsibilities and procedures for ensuring adequate and correct study documentation.

Study data for randomized patients will be entered into an e-CRF by clinical site staff using a secure, validated web-based electronic data capture (EDC) application. Select data for patients not randomized will also be collected in e-CRFs.

Instances of missing, discrepant, or uninterpretable data will be queried with the Investigator for resolution. Any changes to study data will be enacted in the e-CRF and documented in an audit trail, which will be maintained within the clinical database.

